3.2 Exclusion Criteria

Participants who do not fulfill the criteria as listed in [Section 3.1](#) above, are ineligible. Additionally, the presence of any of the following conditions will exclude a participant from study enrollment:

- ___ 3.2.1 Inability to understand and inability to provide informed consent.
- ___ 3.2.2 Participants who are receiving any other investigational agents.
- ___ 3.2.3 Participants who have had anti-neoplastic treatment for KS (including chemotherapy, radiotherapy, local treatment including topical 5-FU, biological therapy or investigational therapy) within 4 weeks (6 weeks for nitrosoureas or mitomycin C) prior to entering the study OR those who have not recovered from adverse events due to agents administered more than 4 weeks earlier.
- ___ 3.2.4 Participants with known brain metastases should be excluded from this clinical trial because of their poor prognosis and because they often develop progressive neurologic dysfunction that would confound the evaluation of neurologic and other adverse events.
- ___ 3.2.5 History of allergic reactions attributed to compounds of similar chemical or biologic composition to sEphB4-HSA or other agents used in study.
- ___ 3.2.6 Concurrent, acute, active infection, or treatment for infection, other than oral thrush, genital herpes, or long-term (i.e., > 1 month) suppression therapy after treatment and clearance of the infection episode (examples include *Coccidioides*, *mycobacterium avium* complex) within 14 days of enrollment.
- ___ 3.2.7 Participants for whom front-line cytotoxic therapy is indicated (i.e., symptomatic visceral or pulmonary KS or symptomatic KS impairing functional status).
- ___ 3.2.8 Concurrent neoplasia requiring cytotoxic therapy.
- ___ 3.2.9 Participant is ≤ 2 years free of another primary malignancy. Exceptions include the following:
 - Basal cell skin cancer
 - Cervical carcinoma in situ
 - Anal carcinoma in situ
- ___ 3.2.10 Any steroid treatment except for that required for replacement therapy in adrenal insufficiency, topical or injected testosterone for hypogonadism, or inhaled steroids for the treatment of asthma.
- ___ 3.2.11 Previous local therapy of any KS-indicator lesion unless the lesion has clearly progressed since that local treatment. Any prior local treatment to indicator lesions regardless of the elapsed time should not be allowed unless there is evidence of clear-cut progression of said lesion.
- ___ 3.2.12 Female participants who are pregnant, lactating, or breastfeeding.
- ___ 3.2.13 Pregnant women are excluded from this study because sEphB4-HSA has not been tested in pregnant women and it could have potential teratogenic or abortifacient

effects. Because there is an unknown but potential risk for adverse events in nursing infants secondary to treatment of the mother with sEphB4-HSA, breastfeeding should be discontinued if the mother is treated with sEphB4-HSA.

- ___ 3.2.14 Participants with a recent history (< 6 months) of a major infarct including but not inclusive to bowel ischemia, cerebral vascular accident, transient ischemic attack, myocardial infarction, limb ischemia, or skin necrosis.
- ___ 3.2.15 Participants with a QTcF (Fridericia Correction Formula) > 480 ms on 2 out of 3 electrocardiograms (EKGs) (if first EKG is < 480, no need to repeat, if first EKG is > 480 repeat twice for a total of 3 EKGs).
- ___ 3.2.16 Participants with systolic blood pressure >120 mm Hg or diastolic blood pressure >80 mm Hg who are unwilling to start antihypertensives (see [Section 5.4](#) for recommendations for management of hypertension during the study), or participants with systolic blood pressure > 140 mm Hg, or diastolic blood pressure > 90 mm Hg, with or without use of antihypertensive medication (participants *may not* enroll onto the study until blood pressure (BP) is \leq 140/90 mm Hg with or without antihypertensive medication).
- ___ 3.2.17 Participants with a recent history (< 6 months) of a major bleed which will be defined as a symptomatic bleeding in a critical area or organ, such as intracranial, intraspinal, intraocular, retroperitoneal, intraarticular or pericardial, or intramuscular with compartment syndrome, and/or bleeding causing a fall in hemoglobin level 2 grams/dL or more or leading to transfusion of two or more units of whole blood or packed red cells.
- ___ 3.2.18 Participants on any dose of warfarin or on full dose anticoagulation with other agents (including low molecular weight heparin, antithrombin agents, antiplatelet agents and full dose aspirin) within 7 days prior to study enrollment; participants on prophylactic doses of low molecular weight heparin and low-dose anticoagulants are allowed.
- ___ 3.2.19 Cardiac related illnesses including, but not limited to:
 - Symptomatic congestive heart failure including participants with grade III/IV cardiac disease as defined by the New York Heart Association (NYHA) functional criteria
 - Unstable angina pectoris
 - Cardiac arrhythmia
- ___ 3.2.20 Proteinuria as defined as \geq 2+ on urine dipstick. If dipstick urinalysis shows \geq 2+ proteinuria, 24-hour urine for protein must be < 2 grams.
- ___ 3.2.21 Participants with diabetes mellitus with ketoacidosis or chronic obstructive pulmonary disease (COPD) requiring hospitalization in the preceding 6 months, or any other intercurrent medical condition that contraindicates treatment with sEphB4-HSA or places the participant at undue risk for treatment-related complications.

- ____ 3.2.22 Physical or psychiatric illness/social situations that in the estimation of the investigator would limit compliance with study requirements or place the participant at high risk of toxicity or non-compliance.

Physician Signature: _____ Date: _____

(Optional unless this section is used as an eligibility checklist)

3.3 Number of Participants to be Enrolled

3.3.1 Proposed sample size

This study will enroll a minimum of 6 participants and a maximum of 20 participants.

3.3.2 Accrual rate

Approximately 1 participant per month.

3.4 Participant Enrollment Procedures

Sites must have this protocol approved by their Institutional Review Boards (IRB) and be registered for study participation with the AMC Operations and Data Management Center (ODMC) before they may enroll participants.

After it has been determined that the participant is eligible and an informed consent form has been signed by the participant, the participant must be registered on-line via the AMC Advantage eClinical Internet Data Entry System (Advantage eClinical) Enrollment and data collection will occur via the AMC Internet Data Entry System.

The participating site will ensure a participant meets all eligibility criteria prior to completing the protocol-specific eligibility checklist in Advantage eClinical for enrollment. Participants will be enrolled on-line via Advantage eClinical no more than 1 week prior to the initiation of treatment (enrollment 1 day prior to or on the day of treatment is strongly encouraged). Once the eligibility checklist is submitted a system-generated confirmation email will be sent to the enroller upon successful completion of the participant enrollment. If the on-line system is inaccessible, the site should notify the AMC ODMC (via email at [contact] or via phone at [contact]) for further instructions.

4.0 TREATMENT PLAN

4.1 Agent Administration

Protocol agents will be administered on an outpatient basis. Appropriate dose modifications for sEphB4-HSA are described in [Section 5.0](#). No investigational or commercial agents or therapies other than those described below may be administered with the intent to treat the participant's malignancy.

Each cycle of sEphB4-HSA will be 28 days. sEphB4-HSA is administered intravenously. Each cycle includes administration of 2 doses of sEphB4-HSA intravenously at 10 mg/kg administered on Days 1 and 15. With protocol versions earlier than 4.0, a 15 mg.kg dose level was used as dose level 1, and has been discontinued as discussed in [Section 2.3.8](#).

Study medications will be dispensed at study entry (Day 1) and at each subsequent study visit. sEphB4-HSA will be administered via intravenous infusion at approximately the same time each day.

Whenever possible, Cycle 1 Day 1 should be scheduled on a Monday due to timing of laboratory and biopsy samples. The doses should be calculated prior to or on Day 1 of each cycle; the dose administered should remain the same throughout a cycle but should be recalculated at the start of the next cycle. Doses must be adjusted if a participant's weight has changed more than 10% from baseline or the prior dose. Otherwise, doses may be adjusted in conjunction with institutional guidelines. When holidays or other scheduling conflicts exist, doses may be delayed, ideally no more than 1 day (see [Section 5.6](#) for additional guidance on management of dose interruptions).

If any participant develops major bleeding or any unexpected grade 4 or greater event on study, accrual will be held until the PI and sponsor assess the need for changes to protocol or consent. Dose modifications for other toxicity will be allowed and are described below. Participants requiring a delay of > 28 days (4 weeks) due to drug related toxicity will be removed from the study.

Table 4-A: Standard dosing

Regimen Description – INITIAL DOSE LEVEL					
Agent	Premedications/ Precautions	Dose	Route	Schedule	Cycle Length
sEphB4-HSA	No premedication*	10 mg/kg	I.V. over 1 hour**	Days 1 and 15	28 days (4 weeks)
*Reactions are not anticipated. If fevers, chills, or a mild allergic reaction occurs, acetaminophen and/or antihistamines (intravenously or orally) may be administered according to the institutional policy and guidelines. For subsequent doses, acetaminophen and/or antihistamines (intravenously or orally) are recommended prior to re-dosing of sEphB4-HSA.					
**Infusion time variation is allowed (1 hour ± 15 minutes)					

Each cycle of the study drug includes administration of 2 doses of sEphB4-HSA during a 28 day cycle. Doses will be administered on Days 1 and 15 but may be delayed up to 48 hours if necessary. If complete response (CR) is achieved, the participant will receive one cycle beyond CR. Treatment may be resumed if KS progresses off treatment after a CR. The participant will resume the previous dose that he/she was receiving when CR was achieved. Participants who achieve PR or SD may continue the treatment at the dose he/she was receiving when PR or SD was achieved, for a maximum of 12 cycles, if the participant and treating physician feel that it is beneficial to continue treatment. The maximum duration of treatment on study is twelve 4-week cycles.

4.2 General Concomitant Medication and Supportive Care Guidelines

Given it is a soluble protein cleared by the reticuloendothelial system, no drug interactions are anticipated with sEphB4-HSA. However, given this drug is still early in its development, the concurrent use of all other drugs, over-the-counter medications, alternative therapies, herbal medicines/tea, or grapefruit juice must be captured in the Concomitant Medications Form in Advantage eClinical. The Principal Investigator should be alerted if the participant is taking any agent known to affect or with the potential to affect CYP450 isoenzymes.

Participants MUST receive medically appropriate care and treatment for HIV infection, including antiretroviral medications. Due to known cytochrome P450 inhibitory effects of protease inhibitors, particularly for ritonavir, the case report form will particularly note the use of ritonavir for HIV management.

In general, concomitant medications and therapies deemed necessary for the supportive care and safety of the participant are allowed, provided their use is documented in the participant records and on the appropriate CRF. Use of aspirin or nonsteroidal anti-inflammatory drugs (NSAIDs) is not permitted. Low-dose prophylactic heparin will be allowed.

The administration of any other therapies intended to treat KS including chemotherapy and biologic agents is NOT permitted. The use of other concurrent investigational drugs is not allowed. Interactions of sEphB4-HSA with antiretroviral therapy and any other drug have not been studied, however drug-drug interactions with other common concurrent medications used in the HIV participants are not anticipated as this is a fusion protein of sEphB4-HSA and is degraded by the reticuloendothelial system.

No prophylactic or supportive care regimens are required for this drug. No significant irritation related to I.V. administration of sEphB4-HSA has been observed at the injection sites. Fever, chills, shakes, itching, rash, hyper- or hypotension, difficulty breathing have been noted in a previous study with this drug, but after evaluation were deemed unrelated to the drug. However, if any of these symptoms occur, slow or interrupt the infusion and administer supportive care, acetaminophen and/or antihistamines (I.V. or P.O.) as per institutional policy and guidelines.

Nausea or vomiting has been reported in patients receiving this agent. Administer supportive care according to the institutional policy and guidelines.

Rash and pruritus generally resolve when drug therapy is discontinued. No drug related significant skin reaction has been observed thus far.

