2.3.8 Dosing in clinical trial

A phase I trial in refractory/relapsed solid tumors has been completed. The following dose levels were tested in the phase I trial: 2.5 mg/kg, 5 mg/kg, 10 mg/kg and 15 mg/kg administered weekly on Days 1, 8, 15, and 22; and 10 mg/kg, 15 mg/kg and 20 mg/kg administered every 14 days (2 weeks) on Days 1 and 15, by I.V. infusion for 60 minutes. The weekly dosing schema and schedule was chosen based on safety of weekly dosing in animal studies of doses up to 30 mg/kg. No DLTs were seen in this weekly dosing, however dose accumulation was noted. Cohorts consisting of 10 mg/kg, 15 mg/kg and 20 mg/kg, with administration every 14 days (2 weeks), were added to the phase I trial, given the dose accumulation noted with weekly dosing. The phase I maximum tolerated dose (MTD) has been reached with 2 of 6 participants, at 20 mg/kg administered every 14 days,

experiencing grade III hypertension that was not responsive to therapy, requiring dose reduction to 15 mg/kg every two weeks, and long half-life of 7 - 10 days. Therefore, the dose of 15 mg/kg every 2 weeks, administered on Days 1 and 15, was initially used as the starting dose in this Phase II trial.³¹

Based on updated data (unpublished communication with VasGene, 8/2018) from other trials with sEphB4-HSA (ClinicalTrials.gov ID NCT03146871), which take into consideration rates of hypertension and drug accumulation, other trials have been modified to use a dose of sEphB4-HSA of 10 mg/kg every 2 weeks. Based on this information combined with initial experience in this study, this trial is amended with protocol version 4.0 to use a dose of 10 mg/kg every 2 weeks, administered on Days 1 and 15 of each cycle. In addition, other unpublished studies (ClinicalTrials.gov ID NCT02717156 and NCT03049618), which dosed sEphB4-HSA at 10 mg/kg weekly, showed grade 3/4 hypertension in 3/21 and 3/19 participants, respectively. Given the updated information of drug accumulation in the context of an approximately 5-day half-life of sEphB4-HSA, the weekly dose will not be used in this trial.

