In the case of grade 3 hypertension as documented by two or more different measurements - that are at least 30 minutes apart and measured by a healthcare provider - treatment with sEphB4-HSA must be held until hypertension returns to target BP (<140/90 mm Hg). Participants should be initiated on antihypertensive therapy, or if already on antihypertensive therapy, participants should have their antihypertensive therapy titrated, per the treating physician. BP should be rechecked 3-5 days after initiation or titration of antihypertensive therapy, or after approximately 5 half-lives to allow antihypertensive drug levels to achieve steady state (~5 days for an antihypertensive dosed daily and ~3 days for one dosed twice daily). If SBP is still ≥ 140 mm Hg and/or DBP is ≥ 90 mm Hg, the antihypertensive dose should be increased, or additional antihypertensive therapy added as indicated. Continue to monitor BP and titrate antihypertensives every 3-5 days until target BP (<140/90 mm Hg) is achieved. sEphB4-HSA should be held until hypertension returns to target BP (<140/90 mm Hg) and patient is asymptomatic, at which point sEphB4-HSA

[figure not shown]
treatment can be resumed.

If after subsequent dosing of sEphB4-HSA, grade 3 hypertension recurs - as documented by two or more different measurements that are at least one hour apart and measured by a healthcare provider - hold sEphB4-HSA and titrate antihypertensives as above until target BP (<140/90 mm Hg) is achieved. When subsequent dosing of sEphB4-HSA is restarted, patient will require reduction of sEphB4-HSA by one dose level.

If patient has to hold treatment for 4 weeks due to hypertension, sEphB4-HSA treatment will be discontinued.

All participants must be educated about the hypertension side effect and instructed to contact the study team if their BP remains under poor control between visits. It is recommended participants keep a BP log, but this is up to the treating physician's discretion.

Hypertension Management Schema

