6.1 Comprehensive Adverse Events and Potential Risks Lists

6.1.1 Adverse event list for sEphB4-HSA

Agent not supplied by CTEP: Please see the investigational brochure for the full details of potential risks.

Table 6-A: sEphB4-HSA expected toxicities:

System Organ Class	Adverse Event Term
General disorders and administration site conditions	Fatigue
Nervous system disorders	Headache
Vascular disorders	Hypertension

Table 6-B: Reported on trials using sEphB4-HSA but with the relationship to sEphB4-HSA still undetermined:

System Organ Class	Adverse Event Term
Gastrointestinal disorders	Nausea
	Vomiting
	Other (hematemesis)
General disorders and administration site conditions	Chills
	Vomiting
	Fever
Neoplasms, benign, malignant and unspecified (incl. cysts and polyps)	Tumor pain
Nervous system disorders	Syncope

Table 6-C: Risks not reported in prior trials of sEphB4-HSA but the occurrence of which will be monitored in this investigation:

System Organ Class	Adverse Event Term
Blood and lymphatic system disorders	Anemia
	Leukocytosis
Cardiac disorders	Left ventricular systolic dysfunction
	Ventricular arrhythmia
	Myocardial infarction
General disorders and administration site conditions	Infusion related reaction
Immune system disorders	Allergic reaction
Investigations	Platelet count decreased
	White blood cell decreased
	Lymphocyte count increased
Metabolism and nutrition disorders	Acidosis
	Tumor lysis syndrome
	Hyperkalemia
	Hyperuricemia
	Hyperphosphatemia
	Hypocalcemia
Musculoskeletal and connective tissue disorders	Arthralgia
	Generalized muscle weakness
	Myalgia
	Myositis
Nervous system disorders	Stroke
	Ischemia cerebrovascular
	Seizure
	Tremor
Renal and urinary disorders	Acute kidney injury
	Proteinuria
Respiratory, thoracic, and mediastinal disorders	Dyspnea
Skin and subcutaneous tissue disorders	Pruritus
	Rash
Vascular disorders	
	Hypotension
	Thrombosis

Note: sEphB4-HSA in combination with other agents could cause an exacerbation of any AE currently known to be caused by the other agent, or the combination may result in events never previously associated with either agent.

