8.2 Evaluations during Treatment

Evaluations must be completed within 7 days prior to day 1 of each cycle, unless another window is noted. See [Appendix I](#) for full details. Dosing should occur on days 1 and 15 of each cycle but may be delayed up to 48 hours, if necessary. Doses delayed by more than 48 hours but less than 28 days due to toxicity or otherwise, require resetting the treatment schedule as outlined in protocol [Section 5.6](#). Evaluations will be completed as outlined below:

8.2.1 Cycle 1

Clinical assessment at Days 1 and 15 of Cycle 1 to include an assessment of the following unless otherwise specified.

8.2.1.1 KS Tumor Assessment: KS tumor assessments will occur on Day 1 of each cycle.

8.2.1.2 Photographic documentation as described in [Appendix VI](#) will be completed at each visit when the KS response category changes. For example, if a participant's KS response category changes from no response to PR, the site will take photos of this to document the category change. If there was no change in the KS response category, no photos are required at that visit. Response of KS to treatment will be assessed as described in [Section 9.1](#).

8.2.1.3 A complete physical exam including: vital signs, weight, toxicity assessment (Day 15), and ECOG or KPS performance status. Vital signs must include blood pressure for evaluation of potential hypertension. Hypertension is a known and expected side effect of this drug. All BP measurements will be obtained after the participant has been sitting in a sitting or supine position for 5 minutes or longer. If the BP is elevated, BP will be repeated with another measurement that is at least 30 minutes apart to account for HP stabilization and variability in participants. If the BP is noted to be transiently elevated (decreases to baseline level during second measurement), the event will be documented in local source, but the BP will not be reported as an AE in Advantage eClinical. Please see [Section 5.4](#) for special considerations for participants with cardiac risk factors and specific instructions for participants who develop \geq grade 2 hypertension while on treatment.

8.2.1.4 If HIV-positive, all HIV-related and AIDS-defining events ([Appendix V](#)).

8.2.1.5 Assessment of adherence to antiretroviral therapy (if HIV positive).

- 8.2.1.6 Review of concurrent medications, including current anti-HIV drugs if HIV positive.

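### Section 4.2 describes hypertension as unrelated to sEphB4-HSA, against Sections 2.3.8, 5.4, 8.2.1.3, Table 6-A and Appendix I; the same sentence also conflicts with Tables 6-B and 6-C

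*Combined protocol and SAP*

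**What the plan says.** Section 4.2, on concomitant medication and supportive care, names fever, chills, shakes, itching and rash and continues: "hyper- or hypotension, difficulty breathing have been noted in a previous study with this drug, but after evaluation were deemed unrelated to the drug". The next sentence tells sites what to do: "if any of these symptoms occur, slow or interrupt the infusion and administer supportive care, acetaminophen and/or antihistamines". It does not refer to Section 5.4.

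The other sections treat hypertension as an effect of the drug:

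- Section 2.3.8, on phase I: "The phase I maximum tolerated dose (MTD) has been reached with 2 of 6 participants, at 20 mg/kg administered every 14 days", these participants "experiencing grade III hypertension that was not responsive to therapy, requiring dose reduction to 15 mg/kg every two weeks". It also gives hypertension rates as one reason for the move to 10 mg/kg every 2 weeks.
- Section 5.4 calls it an expected event for drugs acting on the VEGF pathway and sets actions by blood-pressure grade.
- Table 6-A lists it as an expected toxicity, with fatigue and headache.
- Section 8.2.1.3: "Hypertension is a known and expected side effect of this drug". Appendix I says the same.

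The other terms in the Section 4.2 sentence also appear in Section 6.1.1. Table 6-B places fever and chills among events whose relationship to the drug is undetermined. Table 6-C, titled "Risks not reported in prior trials of sEphB4-HSA but the occurrence of which will be monitored in this investigation", contains pruritus, rash, hypotension and dyspnea.

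**The concern.** Investigators assign attribution event by event, and Section 4.2 is text that sites consult when a participant has symptoms during treatment. It tells them, without qualification, that the toxicity that set the phase I maximum tolerated dose was judged not to be caused by the drug. The safety tables and the blood-pressure section say otherwise.

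Attribution has consequences here. Under Sections 10.1 and 10.2 an unacceptable toxicity enters the primary decision rule only if it is attributed to treatment. The two sections set the threshold differently (at least probable in 10.1, at least possible in 10.2), but an event scored unrelated is excluded under both. Footnote 1 to Table 6-D also makes expedited reporting of serious events more than 30 days after the last dose depend on attribution.

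Table 6-C raises a separate question of fact. Four symptoms cannot both have been noted in a previous study of this drug and never have been reported in prior trials, unless the table silently leaves out events judged unrelated.

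**Working it through.** **1. Terms side by side**

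| Term in Section 4.2 | Status in 4.2 | Status elsewhere | Agree? |
|---|---|---|---|
| Hypertension | Noted, unrelated | Set the phase I MTD (2.3.8); expected class event (5.4); expected toxicity (Table 6-A); known side effect (8.2.1.3, Appendix I) | No, on relationship |
| Fever, chills | Noted, unrelated | Relationship undetermined (Table 6-B) | No, on relationship |
| Itching, rash, hypotension, difficulty breathing | Noted, unrelated | Not reported in prior trials (Table 6-C: pruritus, rash, hypotension, dyspnea) | No, on occurrence |

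Section 4.2 adds a little later that rash and pruritus generally resolve once the drug is stopped. That is hard to square with their never having been reported.

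**2. Hypertension figures in Section 2.3.8**

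- Phase I, 20 mg/kg every 14 days, grade III: 2/6 = 33.3%.
- Two other studies, 10 mg/kg weekly, grade 3/4: 3/21 = 14.3% and 3/19 = 15.8%.

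These come from other doses or schedules and do not forecast the rate in this trial. They show only that the protocol itself treats hypertension as dose-limiting.

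**3. The plan's decision rule (Section 10.2)**

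Inputs: n = 20; reject the null with at least 9 responders and at most 3 unacceptable toxicities; null rates 0.30 and 0.30; alternative rates 0.60 (response) and 0.10 (toxicity). Exact binomial, with response and toxicity taken as independent:

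- P(responders ≥ 9 | 0.60) = 0.9435 and P(toxicities ≤ 3 | 0.10) = 0.8670. Power = 0.9435 × 0.8670 = 0.818; the plan states 0.82.
- P(responders ≥ 9 | 0.30) = 0.1133 and P(toxicities ≤ 3 | 0.30) = 0.1071. The null is met if either rate is unacceptable, so alpha is the larger value, 0.113; the plan states 0.11.

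The stated design reproduces, so the design arithmetic is not at issue. With a limit of 3, one event decides the outcome at the boundary: four qualifying events with one scored unrelated give a count of 3, which passes.

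**4. Which qualifying toxicities Section 4.2 could touch**

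| Category in Section 10.1 | Named or suggested by the 4.2 sentence? |
|---|---|
| Grade 4 hematological toxicity beyond 4 weeks | No |
| Steven-Johnson Syndrome | No |
| Major allergic reaction needing epinephrine | Possibly, through itching, rash, hypotension or difficulty breathing |
| Grade 4 non-hematological toxicity unresolved despite optimal care, including antihypertensive titration | Yes, for hypertension |
| Grade 3 neuropathy of at least 4 weeks | No |

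Two of five categories are plausibly open. Grade 3 hypertension, the grade that set the phase I MTD, is not on the list.

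**The case against.** The strongest reply is that Section 4.2 is infusion-reaction guidance reporting the evaluation made in one unnamed study. On that view it neither instructs investigators how to attribute events in this trial nor competes with Section 5.4. Attribution follows the five categories in Section 6.2.8, adverse events are recorded whatever their relationship, and under Appendix XIII the medical monitor reviews serious events for relatedness and all adverse event listings quarterly.

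Much of this stands. A reader might infer that Section 4.2 allows raised blood pressure to be managed by infusion rate alone. The documents do not support that. Section 4.1 sends dose modification to Section 5.0, and Sections 5.2, 8.2.1.3, 8.2.2.2 and Appendix I send hypertension to Section 5.4. Section 5.4 acts on blood-pressure grade, not attribution. Interrupting an infusion and then applying the grade rule are compatible. What remains is that Section 4.2 names hypertension, gives an action for it and does not point to Section 5.4.

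A reader might also infer that a sizeable share of unacceptable toxicities would be scored unrelated, making acceptance of a toxic regimen much more likely. The documents give no misattribution rate, and applying one to all five categories would ignore that three are untouched.

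Some facts cannot be settled from the documents: which previous study is meant, and whether Table 6-C leaves out events judged unrelated. The part of Section 2.3 between 2.3.6 and 2.3.8 and the hypertension schema are not in the copy reviewed, and Section 6.1.1 defers to the investigator's brochure for full risk details.

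None of this removes the contradiction on attribution. Even if the sentence accurately reports one study, it is misleading as an unqualified statement about the drug in current guidance.

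**Conclusion.** The point holds as an internal contradiction in operative text. Section 4.2 conflicts with five other places in the protocol on whether hypertension is drug-related, with Table 6-B on fever and chills, and with Table 6-C on whether four other symptoms had been seen before. It is more than clerical, because the statement concerns the toxicity that set the phase I MTD and attribution decides which events enter the primary toxicity count.

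The effect on the primary endpoint is narrow. It runs mainly through unresolved grade 4 non-hematological toxicity and possibly through allergic reactions needing epinephrine, and it requires investigators to be influenced by the sentence and later review not to correct them. The documents do not allow it to be quantified. They also do not show that Section 4.2 overrides Section 5.4; on handling, the finding is limited to two unlinked texts that must be reconciled.

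**What to change.** 1. Correct the Section 4.2 sentence so that it no longer describes hypertension as unrelated to the drug.
2. Align fever and chills in Section 4.2 with their undetermined status in Table 6-B.
3. For itching, rash, hypotension and difficulty breathing, have the sponsor establish from its safety data whether they were reported in earlier studies, and make Section 4.2 and Table 6-C agree. Table 6-B does not list these four terms, so its status should not simply be carried over to them.
4. Have the sponsor reconcile the hypertension handling text in Sections 4.2 and 5.4. No clinical rule is proposed here.

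The cost is edits to Section 4.2 and, depending on item 3, Table 6-C, made through a written amendment under Section 12.2, plus the sponsor's check of its safety data. No visits, procedures, participants or changes to the decision rule are needed.
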